2.2.3 Minimization of Risks

Research participants will be carefully screened to meet enrollment criteria. Participants meeting exclusion criteria will not be enrolled. The study participant informed consent will be presented with clear description of the study requirements and opportunity to have questions answered before enrollment. Once an event occurs review of symptoms will be ascertained at 15 and 30 minutes for up to an hour. Reporting of adverse events will be reviewed routinely and in accordance with regulatory guidelines (21CFR, GCP) by the Principal Investigator. Participants with occurrence of worsening symptoms or adverse events should stop taking the test product and may seek medical attention and exit the study.

3 Study Objectives

Beyond the obvious physical symptoms, lifestyle impact related to tension headaches include decreased work productivity and lost work time [17, 18]. The purpose of the present study is to 1) evaluate the impact of the tension relief test product on the symptoms of tension headaches and functional status in adult men and women who suffer from mild to moderate tension headaches by using the 10-point Mankoski scale [19] and 2) the

subjective experience of these participants related to general health, symptoms of tension headaches, and personal experience with the products.

This will be evaluated based on the primary and secondary endpoints. These endpoints, the analysis populations, and their respective measures are described below. Further details on the methods for measuring the outcomes can be found in the Study Outcome Measures and Analysis Plan sections.

Primary Endpoint:

The primary endpoint is reduction in tension headache severity. Patients will be asked to rate headache on the 10-point Mankoski scale at 4 time points: prior to taking the product, 15 minutes after taking the product, 30 minutes after taking the product and 1 hour after taking the product. The improvement in symptoms from baseline will be evaluated on a pairwise basis separately for each time point. P-values will be computed for the improvement.

There is no control group for the primary analysis.

Secondary Endpoints:

- The time to other intervention will be analyzed.
- A longitudinal analysis will be performed for patients who report on more than one incident of headache.
- Comparison against the participant's normal behavior.
- Net Promoter Score.
- Adverse events will be summarized.

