6.4 Adverse Event and Safety Monitoring

Adverse Events (AEs) are defined as any untoward medical occurrences described by the study participant. All AEs will be self-reported and documented on the platform. The AEs will be reviewed by the study team including the remote trial coordinator and study principal investigator and reported according to the IRB requirements. Participants who experience adverse events will be advised to stop taking the test product and seek medical attention.

In the event that a participant experiences an adverse event, the clinical study manager or clinical ops coordinator will notify both the PI and Sponsor. The Sponsor will take appropriate action according to their standard operating procedures for any adverse events that warrant action by the Sponsor.

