6.4.3 Serious Adverse Events

A Serious Adverse Event is an Adverse Event that leads to death or to serious deterioration in the health of the participant that either resulted in a life-threatening illness or injury, or a permanent impairment of a body structure or body function.

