- **3** Annoying enough to be distracting. Mild painkillers take care of it (Aspirin, Ibuprofen).
- **4** Can be ignored if you are really involved in your work, but still distracting. Mild painkillers remove pain for 3-4 hours.
- **5** Can't be ignored for more than 30 minutes. Mild painkillers ameliorate pain for 3-4 hours.
- **6** Can't be ignored for any length of time, but you can still go to work and participate in social activities. Stronger painkillers (Codeine, narcotics) reduce pain for 3-4 hours.
- **7** Makes it difficult to concentrate, interferes with sleep. You can still function with effort. Stronger painkillers are only partially effective.
- **8** Physical activity severely limited. You can read and converse with effort. Nausea and dizziness set in as factors of pain.
- 9 Unable to speak. Crying out or moaning uncontrollably near delirium.
- 10 Unconscious. Pain makes you pass out.

	Afte	r your	headache	resolved	please com	plete any	of the	following	questions i	if applicabl
--	------	--------	----------	----------	------------	-----------	--------	-----------	-------------	--------------

Did your symptoms resolve completely with the test product? Yes No If yes, time of complete symptom resolution:						
Did you need to take another medication: Yes No						
Medication #1:	Dose:	Time:				
Medication #2:	Dose:	Time:				
Medication #3:	Dose:	Time:				
Did your symptoms resolve completely with taking your medication? Yes No						
After taking medication, time of complete resolution of symptoms:						
Did you experience any side effects after taking the test product? (Y/N) If yes, Please fill out the Adverse Event form.						

13.1.6Appendix F Study Exit Form

symptoms? (y/n)

Study Exit

1.	Pleas	e rate y	our ov	erall ex	perience w	ith th	e test	produc	t.	
0 Poor	1	2	3	4	5 Neutral	6	7	8	9	10 Excellent
1a	. Why?	(free r	espons	e)						
2.	Do yo	ou feel t	hat th	e test p	roduct help	ed w	ith yo	ur head	aches i)
0 Not at	all	2	3	4	5 Neutral	6	7	8	9	10 definitely
3. How likely are you to recommend the test product to your friends or family members?										
0 Not Li	1 kely	2	3	4	5 Neutral	6	7	8	9	10 Extremely Likely
4. Do you feel that the test product helped your body cope with occasional tension and occasional head discomfort?										
0 Not at	all	2	3	4	5 Neutral	6	7	8	9	10 definitely
5.		=	_		you like to sistency, or				-	xperience with the sponse)

6. Did the test product help prevent you from having to take any other medication for your

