
13.1.7Appendix G Adverse Event Form

Tension AE document

- 1. Did you experience any side effects after taking the test product? Y/N
 - a. If so, did you experience any of the following
 - o itching, rash, hives, throat/lip/tongue swelling, wheezing
 - low blood pressure, fainting, chest pain, shortness of breath, palpitations, irregular heart beat
 - o severe, persistent nausea, vomiting, diarrhea, or abdominal pain
 - o difficulty urinating, decreased urination
 - o fatigue, appetite loss, yellowing skin/eyes, itching, dark urine
 - severe joint/muscle pain
 - o slurred speech, one-sided weakness of face, arm, leg, vision
 - o abnormal bleeding from nose or gums
 - o blood in urine, stool, vomit,
 - o marked mood, cognitive, or behavioral changes, thoughts of suicide
 - o Other:
- 2. Please give a description of the event
- 3. How soon after taking the test product did you experience the side effect?
- 4. What did you do to alleviate the side effect?
- 5. Did you have to go to the hospital or see a doctor for this side effect?
 - a. Please describe any diagnosis or treatment that they provided.
 - b. If you were seen in the hospital, please upload any discharge paperwork or other documents from the hospital.

13.1.8Appendix H Test Product Insert

Welcome to the Tension Headache Relief Trial!

We appreciate you taking the time to participate in this trial. As you may already know, the aim of this study is to measure the impact the test product has on your headache symptoms. Please take the time to read the following information below to become acquainted with the trial instructions.

Instructions upon Study Product Receipt:

- 1. Please log onto the study portal and acknowledge the receipt by completing the 'Start Form'
- 2. Enclosed in the study bag, please find a 3-episode supply of the tension relief test product.
- 3. You will take the test product the next time you have a headache and need to take something to relieve the discomfort.

Instructions Once Product Intake Begins:

- 1. The next time you have a headache and feel the need to take the test product, you will FIRST start the headache diary (paper forms included in this package).
 - You will complete the date of the episode, the time the episode began, what triggered the headache, type/description of the pain, its location, and record other symptoms (if applicable).
 - REMINDER: DO NOT TAKE ANY OTHER MEDICATION/SUPPLEMENT DURING THE HOUR AFTER TAKE THE TEST PRODUCT.

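### The adverse event form and the visible exit form items do not ask whether an event resolved, whether the product was stopped because of it, or why the participant left, so harm-related stopping cannot be reliably counted

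*Combined protocol and SAP*

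**What the plan says.** Section 6.4 has all adverse events self-reported and documented on the platform, then reviewed by the study team. It also says: "Participants who experience adverse events will be advised to stop taking the test product and seek medical attention". Section 2.2.3 says that participants with worsening symptoms or adverse events "should stop taking the test product and may seek medical attention and exit the study". Section 6.4.3 counts among serious events those that lead to "a permanent impairment of a body structure or body function". Section 6.4.2 has the investigator judge relatedness, severity and causality; outcome and action taken with the product are not listed.

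The self-report instruments are Appendix G (adverse event form) and Appendix F (study exit form). After a yes/no question with a symptom checklist, Appendix G asks: "Please give a description of the event"; "How soon after taking the test product did you experience the side effect"; "What did you do to alleviate the side effect"; and "Did you have to go to the hospital or see a doctor for this side effect", the last with diagnosis, treatment and any hospital papers. Appendix F has six visible items: overall experience with a free-text reason for the rating, help with headaches, likelihood of recommending, coping with tension, a free-text comment on the product, and one that begins "Did the test product help prevent you from having to take any other medication for your".

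The schedule in section 6.2 places an AE assessment at the start of each event, at 15, 30 and 60 minutes, and at Study Exit. The synopsis and section 3 say that adverse events will be summarized. Sections 7.1 and 7.3 specify no table for them.

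**The concern.** The protocol expects some participants to stop the product, and perhaps leave, because of an adverse event. It also has a seriousness criterion that turns on how an event ended. Neither can be read off the data unless something asks for it.

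Two uses of the data are exposed. The first is the safety summary: a count of people who stopped or left because of an event is a basic description of tolerability, and the synopsis says the data may be used to design a two-arm trial. The second is the longitudinal analysis of participants with more than one headache. If people drop out after their first episode because of harm, that analysis is run on those who tolerated the product, and the dropout cannot be identified as such.

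**Working it through.** No sample size, power or event figure is involved, so the check is an item-by-item reading of the two forms, followed by a search for any other route to the same information.

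**Step 1. The forms against the three pieces of information.**

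| Information | Appendix G | Appendix F (visible items) |
|---|---|---|
| Event resolved, ongoing, or lasting effect, with date | Not asked; the timing item covers onset only | Not asked |
| Product stopped because of the event | Not asked; item 4 is about relief of the side effect | Not asked |
| Reason for leaving | Not asked | Not asked; the free-text reason in item 1a explains a product rating |

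That is 0 of 3 on each form. By contrast, the headache diary (Appendix E) does ask for the time at which the headache fully resolved, so a question of this kind already fits the platform.

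**Step 2. Other routes in the protocol.**

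- *AE assessment at Study Exit (section 6.2).* This could pick up an event that is still present. The only visible tool for it is Appendix G, which lacks the items.
- *Study-team and investigator review (sections 6.4 and 6.4.2).* The team reviews each report, and the investigator and sponsor are notified. The listed judgements are relatedness, severity and causality. Section 11 says that the study relies solely on self-report, with no medical review of symptoms.
- *Free text (Appendix G items 2, 4 and 5a; Appendix F items 1a and 5).* A participant may volunteer the outcome or the decision to stop. Nothing prompts for it, so silence cannot be read as a no.
- *Hospital papers (Appendix G item 5b).* These exist only for participants seen in hospital.
- *Coordinator contact at 30 days (section 6.5).* This is triggered when no event information has been supplied. A participant who reported one episode and a side effect need not trigger it. Those who stay unreachable are classed as withdrawn and the exit form is completed for them; that form has no visible reason field.

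**Step 3. Can stopping be inferred from non-use?** Section 6.1 makes episodes 2 and 3 optional, and a participant who completes only the first is exited on day 60. Take two participants who each report a side effect at episode 1 and record nothing further. One stopped because of it; the other had no second headache or chose not to record one. The specified fields hold the same information for both.

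**Step 4. Direction of the error.** Harm-related stops that go unrecorded make the product look better tolerated than it was. The bias, if any, is toward overstating tolerability.

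**The case against.** The strongest reply is that the protocol is not blind to these events. A participant who reports an adverse event has a form with symptoms and timing, the study team sees it, and an AE assessment is scheduled at exit. An adverse event followed by no later dose identifies the candidates for harm-related stopping, and worsening headache shows in the pain ratings. No table of exits due to adverse events is promised, so none is contradicted. The longitudinal analysis is secondary and section 7.1 calls the secondary analyses hypothesis generating. Permanence is a medical judgement that a tick in a 60-day self-report study could not settle.

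Most of this stands and limits the point. A reader might infer that harm-related exits cannot be counted at all and permanence cannot be judged. The documents do not support that, because the routes in step 2 may reveal some cases. Nor does a participant who reported an event look the same as one who simply had no further headache; what is missing is confirmation of the reason.

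A reader might also use the assumption in section 7.2 that half of those enrolled will have no headache in 60 days to argue that non-use is uninformative. That assumption concerns people who never take the product. It says nothing about second headaches among the treated, so the argument rests on the optional status of episodes 2 and 3 alone. Finally, an absent field yields no data, not a recorded count of zero.

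What the reply does not supply is any place where outcome, product stopped or reason for leaving is described as being recorded.

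**Conclusion.** The point holds as a gap in data capture. Stopping or leaving because of harm cannot be reliably counted from the specified fields, and the outcome information needed to apply the permanence criterion in section 6.4.3 is not systematically collected. The safety summary may overstate tolerability. By how much cannot be derived, since the documents give no expected rate of events or of harm-related stopping. The primary endpoint and its analysis are untouched. The change is still worth making before enrollment, because reasons and outcomes that were not asked for cannot be dependably recovered once participants have left.

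The conclusion assumes that the visible items of Appendices F and G are complete. Item 5 of the exit form is broken in the text, and the contents list a section 13.1.9 that could not be read, so a further item or form cannot be fully excluded. If one exists that records these three things, the point falls.

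**What to change.** - **Appendix G:** add an outcome item (resolved, with date; ongoing; resolved with lasting effects) and a yes/no item on whether the product was stopped because of the event. A report of lasting effects should prompt investigator follow-up, since the participant's answer alone does not establish permanence.
- **Study Exit:** at the AE assessment already scheduled there, ask again about every event last recorded as ongoing.
- **Appendix F:** add a reason for leaving, with options that separate completion of three episodes, reaching day 60, a side effect, worse headache, lack of help from the product, and other. Include a category for participants who could not be reached, because section 6.5 has the form completed for them too.
- **AE summary (section 7.3 or the later SAP):** report the outcome of each event and the number who stopped or left because of one.

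The cost is three short items on two electronic forms, about a minute more for participants with an event, and one extra table row. These are recording changes only: no dose, treatment or stopping rule is altered.
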